# APPROACH

**Objective:** The overall objective of this Phase 2 trial is to compare the change from baseline to week 8 of IN- OXT on hyperphagia in children with PWS. We have obtained an IND for the use of IN-OXT for PWS (IND 121109) and will utilize IN-OXT and matching placebo (Manufactured by Novartis as Syntocinon - see letter in appendix regarding batch number and certificate of analysis).

We will also compare the effects of IN-OXT from baseline to week-8 on repetitive behaviors (Repetitive Behavior Scale-Revised - RBS-R), weight, BMI (z-score), and body composition via bioelectrical impedance analysis, quality of life (World Health Organization Quality of Life scale – WHOQOL and Caregiver Strain Questionnaire -CSQ), salivary oxytocin concentration, and safety measures. Safety will be assessed with monitoring of routine laboratory tests and levels of testosterone and estrogen, physical exam, urine pregnancy test for menstruating females, and collection of vital signs. The Aberrant Behavior Checklist (ABC) will also be used as a safety measure for both suicidality (per FDA guidelines) and for adverse events (aggression/temper tantrums). In addition, we will monitor measures of hypogonadism and sleep apnea throughout the study. This Phase 2 study is designed to generate preliminary data for future Phase 3 trials, and targets symptoms in this population that currently have no effective treatments. By treating these symptoms earlier in life in a pediatric PWS population we may maximize the treatment impact.

This study supports the Orphan Product Divisions goal of identifying and promoting the development of treatments indicated for rare diseases or conditions. Our proposed treatment

will target hyperphagia in subjects with PWS, a symptom for which there is currently no effective treatment. This study will provide essential data that is needed for drug development and eventually drug approval.

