**Research Strategy And Feasibility:** We propose a three year, phase 2, randomized doubleblinded 8-week treatment trial of IN-OXT vs. placebo in 50 child and adolescent subjects (25 male and 25 female) aged 5 to 17 years with a diagnosis of PWS. PWS diagnosis will be confirmed by study team via patient interview and confirmation by patient's past medical records and genetic testing results. At the screening visit, patient will have the opportunity to learn about the study and seek clarification on any outstanding questions. If patient voluntarily agree to participate, study team will work with the patients to complete the informed consent and if applicable, assent. In addition, a psychiatric interview and medical history review will be conducted to screen the patient for eligibility. The study team will also review patient's concomitant medications, assess for patient condition with CGI-S and hyperphagia using the Hyperphagia Questionnaire-Clinical Trials (HQ-CT). If patient meets selection criteria, the study team will arrange on behalf of the patient for an out-patient Quest visit, at which time patient will be asked for a screening blood draw to provide information on CBC, BMP, LFT, IGF-1, thyroid panel, lipid panel, testosterone, estrogen, hemoglobin A1C, and for applicable patient, a urine pregnancy test. Once the screening blood work results are available and all results are within acceptable range, and patient is otherwise eligible, patient will be invited for an in person visit to clinic where additional assessments including a complete physical and neurological exam, intelligence test, interval health or medication change, and if applicable, repeat urine pregnancy test will be conducted. If patient continues to meet all study inclusion and exclusion criteria and agrees to continue with study participation, the study team will formally submit the patient for randomization. The randomization is done in a 1:1 placebo to oxytocin ratio and stratified for gender. The result is blinded to the study team and the process is performed by the study pharmacist at the Clinical Research Pharmacy using a computer generated randomization table. Patients will receive a supply of oxytocin spray bottle with each spray dispensing 4 IU, or a matching placebo. The participant will start with an initial dose of 2 sprays per nostril (4 sprays per day), or 16 IU/day IN-OXT or placebo. To allow for optimization for adverse events or lack of response, we allow for one downward titration to 12 IU (3 sprays per day), and one upward titration to 24 IU (6 sprays per day) at week 2. This will also allow us to examine the relationship between weight based dosing and treatment response. Syntocinon (synthetic intranasal oxytocin) and matched placebo made by Novartis will be used in this protocol. We have an IND for the use of IN-OXT in PWS (IND 121109).

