#### Titration Schedule:

Adverse events: Study physician will review with study participants regarding the nature,

duration and severity of noted adverse events. The study physician will make clinical judgements on the relationship between reported adverse events with study medication. If there is a high likelihood of adverse events being related drug effects, the subject will titrate down from 16 IU/day (4 sprays per day) to 12 IU/day (3 sprays per day) and will be reassessed in one week). At the next assessment the side effects and tolerability will again be reviewed by the PI and medical monitor. If the side effects have resolved, the subject will be titrated back up to 16 IU/day. If the side effects persist, the subject may continue on the 12 IU/day for another week; or will be discontinued from the study at the judgement of the PI. Subjects who do not receive the full dose by week four will be discontinued. Any subject who is discontinued from the study will be referred for continued medical follow up.

Lack of response: One upward titration will be allowed at week 2 to 24 IU/day (4 sprays per day) if study clinician, with consultation of the PI, determines that study subject experiences no response on hyperphagia via a categorical yes/no determination, and has no adverse events. In our current ongoing pilot study, and in [name]'s study, the initial hyperphagia response was observed at the week 1 and week 2 ratings.

**Instructions for Dosing:** Once the cap has been removed from the spray, the device should be held upright to the nostril and the actuator depressed. The patient should be in the sitting position and should be instructed to inhale gently through the nose while the actuator is being depressed. The head should be tilted back once the actuator is depressed to ensure that no fluid runs out of the nose. Parents may assist the child with dosing.

**Outcome Measures:** Project outcomes will be determined by changes in scores of parent and clinician rated measures from baseline to week 8 and comparisons of week 8 measures between active treatment and placebo groups. Assessments will be administered according to the schedule of events in **Table 2**.

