Safety monitoring will be completed at each visit in both remote and in-clinic settings. Participant will complete concomitant medication review, adverse event (AE) monitoring, ABC rating, and be monitored for hypogonadism, sleep apnea and lethargy, In addition, a complete physical and neurological exam and full panels of clinical labs (CBC, BMP, LFT, IGF-1, thyroid panel, lipid panel, HbA1C, testosterone, estrogen, growth hormone, ghrelin, pancreatic polypeptide, peptide YY, leptin, GLP-1, insulin and glucagon) will be completed at baseline and week 8 in person visits.

For participants who are able to provide salivary samples and co-operate with the collection process, the study team will attempt to obtain pre- and 1 hour post- study IP administration saliva at baseline, week4, and week 8 using the Oragene-Discover collection kit (ORG-500). The salivary samples will be used to measure patient oxytocin levels.

As required by the Division of Psychiatry Products and suggested by FDA review, we have also included the ABC-I subscale at every visit as a prospective assessment for suicidal ideation. The ABC will also be used to assess for adverse events, including increased aggression or temper tantrums. Urine pregnancy tests will be completed at every visit to ensure subject safety. If a subject becomes pregnant during the study, she will immediately be discontinued from the medication. All subjects must use abstinence or a valid method of non-estrogen based double barrier contraception to participate in the study.

While some of these secondary measures have not been studied in PWS, we believe that they

are appropriate for this population as a valid measure of treatment efficacy and focus on important target issues of PWS – including repetitive behaviors (Repetitive Behavior Scale-Revised). The WHOQOL is a validated measure used to assess quality of life and has been used in a vast array of clinical trials in varied disorders (muscular dystrophy, hypertension, tuberculosis, etc.). The Caregiver Strain questionnaire (CSQ) is a commonly used and well-validated self-report questionnaire developed to assess caregiver strain for families with a child living with an emotional or behavioral disorder. The ABC has been used to assess disruptive behaviors in other disorders such as Down Syndrome and other intellectual disabilities

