**Study Time Commitment and Reduction of Burden:** Every effort to reduce the time burden on patients and caregivers has been made. In the era of COVID-19 pandemic and travel restriction, we are implementing telemedicine for remote visits in some of the study visits to reduce patient's potential exposure and travel, while ensure adequate study monitoring are in place.

The HQ-CT, ABC, WHOQOL, CSQ, MERS-PWS and RBS-R assessments are completed with the parent and not the patient, as specified in the schedule of events. As is the case in most clinical trials, the most significant burden to the parent and child is the screening visit, which is done remotely and avoided participant's need to travel. Each parent questionnaire takes between 5 and 25 minutes to complete and child assessments are kept to a minimum, with optional breaks to maximize patient comfort. Screening lab work will be done locally at participants nearest Quest lab. This is particularly beneficial for out of state participants. Clinical lab works are collected only at in person visits at baseline and week 8 during in person clinic visits. We have eliminated the eye- tracking measures as they are not central to our hyperphagia and repetitive behavior aims and to reduce burden. This ensures minimal burden to the family and decreases the time commitment while reducing testing bias on measures. As parent rated measures are questionnaires, no repeat testing bias is expected.

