Psychiatric Interview	30 min	Parent/Child/Cli nician	х						
Intelligence Test	60 min	Clinician/ Child		Х					
Randomization	0 min			Х					
Concomitant Medications	5 min	Parent/Child/Cli nician	х	х	х	x	х	х	Х
Adverse Events/Monitoring for hypogonadism, sleep apnea, lethargy	10 min	Parent/Child/Cli nician	x	х	x	x	x	х	x
Standard Laboratory Tests*	10 min	Clinician/ Child	X***	Х				Х	
Hormone and Metabolic Laboratory Tests**	10 min	Clinician/ Child		х				х	
Treatment Given	10 min	Parent/Child/Cli nician		х		x		х	
Urine Pregnancy Test (if appropriate)	5 min	Child/Clinician	х	Х				х	
Vital signs	15 min	Clinician/ Child		Х				Х	
Eating Behavior Measures									
Hyperphagia Questionnaire- Clinical Trials (HQ-CT)	15 min	Parent/Child/Cli nician	х	х	x	x	х	x	х
Weight, Body Composition and BMI	5 min	Parent/Child/Cli nician		х				х	
Dietary Diary ASA24 Automated Self-	15 min	Parent		х				х	

Administered 24 Hour Recall									
Repetitive Behavior Measures									
Montefiore-Einstein Rigidity Scale –Revised (MERS-PWS)	15 min	Clinician		х		х		x	х
RBS-R	15 min	Parent		X [pre-dose]		х		x	х
Oxytocin Measures									
Salivary Oxytocin Levels	10 min	Clinician/Child		X [pre- and 1 hour post dose]		X [pre- and 1 hour post dose]		X [pre- and 1 hour post dose]	x
Global Clinical Improvement and Quality of Life Measures									
ABC-I (Full ABC will be completed to measure this subscale)	25 min	Parent		X [pre-dose]	х	х	х	x	х
CGI-I	5 min	Clinician			X	Х	Х	Х	Х
CGI-S	5 min	Clinician	Х	Х					
WHOQOL	20 min	Parent/Child/ Clinician		Х		х		x	х
Caregiver Strain Questionnaire	10 min	Parent		Х		Х		Х	х

\* Standard Laboratory Tests: CBC, CMP including sodium, IGF-1, thyroid panel, lipid panel, hemoglobin A1C, and urine pregnancy test
 \*\* Hormone and Metabolic Laboratory Tests: testosterone, estrogen, growth hormone, ghrelin, pancreatic polypeptide, peptide YY, leptin, GLP-1, insulin, glucagon

\*\*\* To be done at local Quest

Table 2: Intranasal Oxytocin vs. Placebo for the Treatment of Hyperphagia in Prader-Willi Syndrome SCHEDULE OF EVENTS

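### The safety text promises a pregnancy test at every visit, but Table 2 schedules none between baseline and week 8, leaving an 8-week untested interval on drug

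*Combined protocol and SAP*

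**What the plan says.** The safety-monitoring text under Outcome Measures sets a frequency and a consequence. The frequency is: "Urine pregnancy tests will be completed at every visit to ensure subject safety". The consequence is: "If a subject becomes pregnant during the study, she will immediately be discontinued from the medication".

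The same part of the protocol hands visit timing to the schedule: "Assessments will be administered according to the schedule of events in" Table 2. The burden section also sends the reader to Table 2 for the content of each visit.

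In Table 2, the row that begins "Urine Pregnancy Test (if appropriate" is marked at screening, baseline and week 8. It is blank at weeks 2, 4, 6 and 10. A footnote lists the pregnancy test among the standard laboratory tests, and that row is marked at the same three visits.

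The Approach section defines who is tested: "urine pregnancy test for menstruating females". The Research Strategy paragraph includes the test in the screening laboratory work ("and for applicable patient, a urine pregnancy test") and repeats it, where applicable, at the in-person visit before randomization.

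**The concern.** The text and the schedule cannot both be followed, and site staff will normally work from the schedule. Staff who do so will omit a safety test that the protocol promises, for the whole of the dosing period.

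The promised test supports a rule that stops drug on pregnancy. Exclusion 8 says that intranasal oxytocin lacks data in pregnancy and lactation, and the subjects are minors. Under Table 2, a girl could have her dose raised to 24 IU/day at week 2 and be given treatment again at week 4 with no test at either visit. What is at stake is how long a girl might continue on drug with an undetected pregnancy. The efficacy result is not at stake.

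**Working it through.** No stated figure needs reproducing. The check sets the two instructions side by side, visit by visit.

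| Visit | Setting | Test under the safety text | Test under Table 2 | Treatment marked in Table 2 |
|---|---|---|---|---|
| Screening | remote | yes | yes | no |
| Baseline | in person | yes | yes | yes |
| Week 2 | remote | yes | no | no |
| Week 4 | remote | yes | no | yes |
| Week 6 | remote | yes | no | no |
| Week 8 | in person | yes | yes | yes |
| Week 10 | remote | yes | no | no |

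**Is the row read correctly?** The physical examination and vital signs rows show the same run of blanks between their baseline and week 8 marks. The blanks are therefore not an artefact of the table's layout.

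**Counts**
- Tests promised: 7 of 7 visits. Tests scheduled: 3 of 7.
- Strictly between baseline and week 8: 3 promised (weeks 2, 4, 6), 0 scheduled.

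**Longest untested interval on drug**
- Under the safety text, tests fall on days 0, 14, 28, 42 and 56, so the longest gap is 14 days.
- Under Table 2, tests fall on days 0 and 56, so the gap is 56 − 0 = 56 days.
- A pregnancy that becomes detectable just after baseline could wait up to 56 days for a scheduled test, instead of up to 14.

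**Who is affected**
- The Research Strategy paragraph plans 25 females. It adds: "The randomization is done in a 1:1 placebo to oxytocin ratio and stratified for gender". Girls on oxytocin: 25 / 2 = 12.5, so about 12 or 13.
- The test applies only to menstruating girls. The age range starts at 5, so 25 is a ceiling.
- The number past menarche and the probability of pregnancy are not given, so no expected number of exposed pregnancies can be calculated.

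**After the change**
- Adding weeks 2, 4 and 6 gives 6 of 7 visits and a longest on-drug gap of 14 days. Adding week 10 as well gives 7 of 7 and the same gap.

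**The case against.** The strongest reply has four parts.

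**Other safeguards exist.** Pregnancy is tested for at screening and again before randomization, contraception or abstinence is required, and adverse events and medications are reviewed at every visit. The stop rule is worded around becoming pregnant, not around a positive test, so a reported pregnancy would also trigger it. This stands. A reader might infer that the stop rule is inoperative without interim tests, and the documents do not support that. These measures still do not replace the test that the protocol itself promises.

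**A week 8 test is not too late for every dose.** A reader might infer that no scheduled test could prevent any dosing. Table 2 marks treatment at week 8 as well, with saliva taken before and after the dose. A test done before that dose could prevent it, though none of the earlier doses.

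**Remote visits partly explain the blanks.** The burden section confines clinical laboratory collection during the trial to the in-person baseline and week 8 visits. A reader might argue that screening disproves this, because it is remote and still has the test: "Screening lab work will be done locally at participants nearest Quest lab". That comparison is weak, since the screening trip is already needed for a blood draw. The week 4 saliva sample is also weak evidence that the child will be at hand: the team only attempts it, in participants able to cooperate. Remote conduct may explain how the mismatch arose, but it does not resolve it. The special-circumstances section allows samples to be taken elsewhere but schedules no pregnancy test.

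**The text could be trimmed to match Table 2.** Nothing in the documents shows that two-weekly testing is necessary in an 8-week trial; the case for it is the protocol's own promise. Trimming would remove the contradiction, but at the price of withdrawing that promise and leaving eight weeks of dosing without an interim test.

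**Conclusion.** The point holds as a mismatch between the promised and the scheduled safety testing. Following Table 2 means 3 tests instead of 7, none strictly between baseline and week 8, and a longest untested interval on drug of 8 weeks instead of 2. Detection before week 8 would depend on a pregnancy being reported or suspected, for example at the adverse event review.

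These counts rest on the current text alone and need no assumption beyond visits taking place on their nominal days. The number of girls at risk is unknown below the ceiling of 25. The event may be rare, since the titration plan names hypogonadism as a known co-morbidity.

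A reader might extend this into a doubt about the trial's results. The documents give no ground for that: the sample size, power and HQ-CT comparison are untouched. It is a subject-safety correction that should be made because it is specific and cheap.

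**What to change.** **Change to make**
1. In Table 2, add the urine pregnancy test for menstruating girls at weeks 2, 4 and 6, by a home kit handed out at baseline or at a local laboratory.
2. Record the result at the remote visit, with a confidential route for the minor's result, because the burden section has these calls held with the parent.
3. On a positive result, stop drug pending confirmation. A missed test prompts a repeat.
4. At week 8, do the test before that visit's dose.
5. For week 10, either add the test or limit the safety text to visits through week 8. A week 10 test could detect a late on-treatment conception but cannot prevent dosing.

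The contraception wording needs no change for this purpose. The safety text applies that requirement to all subjects, so narrowing it to girls would release male subjects from it.

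**Cost**
- Kits: 3 × 25 = 75 at most, or 4 × 25 = 100 with week 10.
- Time per girl, at Table 2's 5 minutes per test: 3 × 5 = 15 minutes, or 4 × 5 = 20 with week 10.
- A home test is less controlled than a clinic test, and a false positive would interrupt drug until it is corrected.
- The local-laboratory route adds trips that the burden section tries to avoid.
- The girl must be available around the time of the calls.

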#### **PRIMARY OUTCOME:**

**Hyperphagia Questionnaire-Clinical Trials (HQ-CT)**: The Hyperphagia Questionnaire-Clinical Trials (HQ-CT) is the standard for assessing how potential therapies may impact hyperphagia in PWS clinical trials. It is a caregiver-rated assessment comprised of 9-items that measure and track the food seeking behaviors and drive for food that is associated with PWS. The HQ-CT is a modified version of the [name]-Hyperphagia Questionnaire (a well-established questionnaire), with changes based on industry and regulatory standards (e.g., Food and Drug Administration, 2009). These modifications included a reduced recall period, optimization of response scales, and limiting item content to observable behaviors that have the potential to change during the course of a clinical trial. Psychometric evaluation demonstrated the HQ-CT's reliability and validity, and the HQ-CT total score has demonstrated improvements in hyperphagia-related behavior between treatment groups in children with PWS. The HQ-CT will be administered at screening, baseline, and at all subsequent visits. In order to be eligible to participate in the trial, scores on the HQ-CT will need to be at least of moderate severity at both screening and baseline visits. It will take about 15 minutes to complete.

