#### **Inclusion Criteria:**

- 1. Male or female pediatric outpatients aged 5 to 17 years.
- 2. Must be in PWS nutritional phase 2b or 3 as determined by PI.
- 3. Must be on growth hormone treatment and have been receiving stable dose of growth hormone treatment for at least three months prior to screening date. Treatment cannot have been interrupted for more than one week within 3 months of screening.
- 4. Diagnosis of PWS confirmed by exam, genetic testing and patient medical records.
- 5. A score of at least moderate severity on the Hyperphagia Questionnaire-CT at both screening and baseline visits
- 6. Stable dosages of hormone treatments (including testosterone and estrogen supplements) for 4 weeks prior to randomization and for the duration of the study.
- 7. Stable dosages of metabolic treatments that could affect appetite (including metformin)

for 4 weeks prior to randomization and for the duration of the study.

- 8. Stable pharmacologic, educational, behavioral and/or dietary interventions for 4 weeks prior to randomization and for the duration of the study.
- 9. Physical exam and laboratory results that are within the normal range for individuals with PWS.
- 10. Presence of a parent/caregiver/guardian that is able to consent for their participation and complete assessments regarding the child's development and behavioral change throughout the study.

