Measurements obtained at a specific time point (e.g. 8 weeks) will be compared between the IN-OXT and placebo groups with the two sample t-test or Wilcoxon rank sum test. In addition, the change in outcome measures between baseline and 8 weeks will be compared between

treatment groups. Exploratory analyses will first be performed to evaluate whether the magnitude of changes in these variables between the two time points depends on the baseline value. If there is no evidence that change is dependent on baseline, then two sample tests will be used to compare the mean change in each variable between treatment groups; otherwise, analysis of covariance models will be fit to the data where the outcome is the level measured at 8 weeks, and the main effects are treatment group and baseline value [15;37]. Adjustment for any patient characteristics which appear to be imbalanced across treatment groups will be accomplished by including the relevant terms as additional covariates into the model. To compare longitudinal trends in outcomes between treatment groups, linear mixed effects models will be fit to all repeated measures obtained during follow-up, with main effects for time and treatment group and a time x treatment interaction term; this is a widely used statistical approach in longitudinal studies of psychiatric outcomes. Appropriate data transformations, such as the log transform, will be applied if the data deviate from the normal distribution. Although a number of different outcomes will be analyzed, we will not adjust for multiple testing given the exploratory nature of this study.

Additional subgroup analyses will also be performed to evaluate and compare treatment effects in males and females. Given the limited sample size of this Phase 2 trial, however, any subgroup analyses will be viewed as exploratory.

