#### **Detailed Description of Analyses**

**Primary Analyses**: Analyses for Specific Aim (1): To compare IN-OXT vs. placebo with respect to improvement in the hyperphagia severity in children with PWS via improvement in scores on the Hyperphagia Questionnaire-Clinical Trials.

The primary analysis will evaluate the hypothesis that IN-OXT will decrease hyperphagia vs. placebo.

- 1. Response to treatment will be assessed in two ways:
  - a. The effects of IN-OXT on hyperphagia will be analyzed using an intent-totreat approach with the two-sample T-test or Wilcoxon rank sum tests to compare treatment groups at specific visits as well as linear mixed effects models to analyze the repeated measures and changes over time.
  - b. The proportion of responders in each treatment group will also be compared. Response will be defined as a 30% or greater decrease in food-seeking and eating behaviors from baseline on the Hyperphagia Questionnaire-Clinical Trials. Dropouts for clinical reasons will be coded as non- responders. Differences in the proportion of responders in each treatment group will be evaluated using the chi-square test and time to response will be assessed using survival analytic techniques.
  - c. All tests will be two-tailed with an alpha level of 0.05.

**Secondary Analyses:** Analyses for Specific Aims (2) through (8): To compare IN-OXT vs. placebo in children with PWS on change in:(2) Repetitive behaviors via scores on the Repetitive Behavior Scale – Revised (RBS-R) and Montefiore-Einstein Rigidity Scale-Revised (MERS-PWS)(3) Weight and body composition via impedance analysis. (4) Quality of Life Measures on the World Health Organization Quality of Life Scale (WHOQOL)(5) Clinical Global Impression Scale (CGI-I) (6) Salivary Oxytocin Concentration (7) Safety Analyses

IN-OXT and placebo groups will be compared to the above secondary measures will be analyzed using methods similar to those outlined above. Associations between outcome measures at a specific time point will be analyzed with the Spearman rank or Pearson correlation coefficient.

- 1. Secondary Aim (1) Repetitive Behaviors
  - *a.* The effects of treatment on frequency and severity of repetitive behaviors will be assessed by fitting linear mixed effects models to the data on the RBS-R scores. We hypothesize that IN- OXT will significantly reduce repetitive behaviors from baseline to endpoint compared to Placebo.

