**Power Analysis: Sample size justification:** The target sample size for this Phase 2 trial is 25 patients per treatment group. The power for the study has been calculated to generate a detectable signal with the sample size of 50 subjects. With this sample size, the study will have 80% power to detect a minimum effect size of d= 0.8 standard deviations in the outcome measures between groups using a two-sample T-test and a two sided Type I error rate of 5%. The study is powered based on a conservative estimate from a heterogeneous population. We expect that in this homogeneous PWS population selected to match study drug to underlying mechanism, the true power will exceed the conservative estimate. This minimum detectable difference is smaller than the treatment effects observed in our previous studies of IN-OXT in adults with ASD, which demonstrated an effect size of d=1.2 on a social cognition measure (RMET) [3], and an effect size of d = 0.84 on a quality of life measure (WHOQOL) [3]. In addition, our previous study of a V1a antagonist in adults with ASD demonstrated an effect size of d=0.8 on a social cognition measure (ASR Lust) [80], and an effect size of d = 0.8 on an Eye Tracking measure (Biological Motion Preference) [90]. The above effect sizes observed in our pilot data were based on a heterogeneous sample of ASD patients characterized by over 100 known different genetic contributing factors. In the proposed trial, both males and females will be included, and any heterogeneity in outcomes due to gender may attenuate overall treatment differences. However, by selecting an orphan population (PWS) with a single unique genetic contribution, and selecting a treatment that matches the known molecular mechanism (IN-OXT), we expect that the treatment effects in this study will nevertheless be greater than the effects observed in earlier studies.

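### The screening HQ-CT score is collected on every randomised child but enters no efficacy analysis; adding it as a second covariate beside baseline may gain modest precision at almost no cost

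*Combined protocol and SAP*

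**What the plan says.** **Collection.** Under Primary Outcome: "The HQ-CT will be administered at screening, baseline, and at all subsequent visits". The schedule of events (Table 2) agrees. Inclusion criterion 5 requires "A score of at least moderate severity on the Hyperphagia Questionnaire-CT at both screening and baseline visits". Screening is a remote visit; baseline and week 8 are in person.

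**Use in the analysis.** The Summary of Analytic Approach and the Primary Analyses list several comparisons for HQ-CT:

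- Two-sample tests of the scores at particular visits, including week 8. No pre-dose score enters these.
- A comparison of change from baseline to week 8.
- An ANCOVA, fitted only if an exploratory look suggests that change depends on baseline, in which "the outcome is the level measured at 8 weeks, and the main effects are treatment group and baseline value".
- A linear mixed model of the follow-up measurements with time, treatment and their interaction. No pre-dose covariate is named.
- A responder comparison: "Response will be defined as a 30% or greater decrease in food-seeking and eating behaviors from baseline".

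The plan also allows covariates for patient characteristics that look imbalanced, but does not name the screening HQ-CT among them. The only stated use of the screening score is eligibility.

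**Power.** The Power Analysis states: "The target sample size for this Phase 2 trial is 25 patients per treatment group". With that number, "the study will have 80% power to detect a minimum effect size of d= 0.8 standard deviations in the outcome measures between groups".

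**The concern.** HQ-CT is a caregiver rating, so one rating is likely to contain some visit-to-visit error. A second pre-dose rating can carry information about the child's underlying level that the first misses. If it does, a model using both predicts week 8 better, leaves less residual variance and gives a narrower interval for the treatment difference.

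This matters here because the trial is small, the power statement reaches 80% only for a large effect, and the sample size has no allowance for dropout. A score already in the database is the cheapest place to look for precision.

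**Working it through.** **1. The plan's own figure.** Inputs from the Power Analysis: 25 per arm, d = 0.8, "using a two-sample T-test and a two sided Type I error rate of 5"%. Allocation is equal (Research Strategy and Feasibility).

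- Noncentrality: 0.8 × √(25/2) = 2.83.
- Power: 80.7% by the normal approximation, 79.1% by the noncentral t with 48 df.

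The stated 80% reproduces. It does not depend on how many pre-dose scores are used.

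**2. What must be assumed.** The documents give no HQ-CT correlations and no interval between screening and baseline. Let p be the screening-baseline correlation, b the baseline-week 8 correlation and s the screening-week 8 correlation. In units of the week-8 variance, the ANCOVA residual is:

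- baseline only: 1 − b²
- baseline and screening as separate covariates: 1 − (b² + s² − 2bsp)/(1 − p²)

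**3. Equal correlations (p = b = s = r).** The second formula becomes 1 − 2r²/(1 + r).

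| r | Baseline only | Both scores | Saving |
|---|---|---|---|
| 0.5 | 0.750 | 0.667 | 11% |
| 0.6 | 0.640 | 0.550 | 14% |
| 0.7 | 0.510 | 0.424 | 17% |
| 0.8 | 0.360 | 0.289 | 20% |

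**4. Truncation at entry.** Both scores must pass a severity threshold, which narrows their range. Simulating a cut on both scores at the 25th or 40th percentile (assumed), with underlying r of 0.5-0.8, leaves a saving of about 6-16%.

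**5. Screening more weakly related to week 8 than baseline is.** This is plausible, since screening comes earlier.

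| p / b / s | Baseline only | Both scores | Saving |
|---|---|---|---|
| 0.75 / 0.65 / 0.60 | 0.578 | 0.549 | 5% |
| 0.7 / 0.6 / 0.5 | 0.640 | 0.627 | 2% |
| 0.8 / 0.7 / 0.6 | 0.510 | 0.506 | 0.9% |
| 0.8 / 0.6 / 0.48 | 0.640 | 0.640 | 0% |

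In the last row s = p × b (0.8 × 0.6 = 0.48), so screening carries nothing about week 8 beyond baseline.

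**6. Power.** Suppose d = 0.8 is measured against the baseline-adjusted residual SD. A saving v turns d into 0.8/√(1 − v).

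- v = 6%: d = 0.825, power about 82%.
- v = 16%: d = 0.873, power about 86%.

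If d is instead measured against the raw week-8 SD, baseline-only ANCOVA already has about 89% power at r = 0.5 and 97% at r = 0.7. Screening then takes these to about 92% and 99% under equal correlations, roughly 2-3 points.

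**7. Cost.** With 50 children, residual df fall from 47 (50 − 3) to 46. Allowing for chance imbalance in the covariates, the expected variance of the treatment estimate rises by (1 + 2/45)/(1 + 1/46) = 1.022, about 2%, if screening adds nothing.

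**8. Averaging the two scores instead.** Change-score variance is 2(1 − b) from baseline alone and 1 + (1 + p)/2 − (b + s) from the mean of the two.

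- Equal correlations: 1.5(1 − r) against 2(1 − r), a 25% saving.
- 0.8 / 0.6 / 0.48: 0.82 against 0.80, 2.5% worse.
- 0.7 / 0.7 / 0.49: 0.66 against 0.60, 10% worse.

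**The case against.** Taking the baseline-visit score as the baseline is conventional and matches the stated aim. The gain depends on correlations that nobody has reported here and may be nil. The larger gap is that no single baseline-adjusted primary model is pre-specified: at r = 0.7, adjusting for baseline alone removes 49% of the week-8 variance, and adding screening brings that only to about 58%. All of this stands. It is why the point is framed as an efficiency and why the fix settles baseline adjustment as well.

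The remote setting of screening is a weaker objection to a separate covariate. A shift in level common to both arms does not matter, because screening has its own coefficient. It is a fair objection to averaging, which would mix a remote score into a contrast that now compares two in-person scores.

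Three stronger readings are tempting but unsupported:

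- *The power statement is wrong.* It reproduces, and it does not involve the number of pre-dose scores.
- *Selecting on a high baseline biases the result through regression to the mean.* Both randomised arms regress alike, so the comparison is not biased. Averaging would not remove the regression either, since both scores are selected.
- *Using both scores cuts variance by 25% and lifts power to about 89%.* That figure belongs to the averaged change score, and only under equal correlations. Step 8 shows that averaging can lose precision.

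**Conclusion.** The point holds as a missed efficiency. Two pre-dose HQ-CT scores exist for every randomised child, and the screening score has no role beyond eligibility. The plausible saving in ANCOVA residual variance runs from nil to about 20%: 11-20% under equal correlations of 0.5-0.8, 6-16% once truncation at entry is allowed for, and 0-5% if screening is the weaker predictor of week 8. The move from 79% to about 82-86% power applies only to the 6-16% range, and only if d = 0.8 refers to the baseline-adjusted residual SD, which the Power Analysis does not say. Every one of these ranges rests on assumed correlations.

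**What to change.** In the Summary of Analytic Approach and the Primary Analyses, for HQ-CT:

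1. Pre-specify the week-8 ANCOVA, rather than making it depend on an exploratory look at the data, with treatment, baseline HQ-CT and screening HQ-CT as separate terms.
2. Enter the same two covariates in the mixed model, and state that its outcomes are the post-baseline scores only, so that baseline does not appear on both sides.
3. Keep the baseline-visit score as the reference for the change score and the 30% responder rule. Do not average it with the remote screening score, except possibly in a labelled sensitivity analysis.

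The change should be made before unblinding. It needs a revision of the analysis text but no new data, visit or procedure. The statistical cost is one degree of freedom, about 2% in precision in the worst case shown above.
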